**University Hospitals Case Medical Center**  
**Department of Dermatology**  
**Protocol**

**Protocol Title:** Effects of UVB Excimer Laser on Serum Inflammatory Markers in Patients with Psoriasis

**Principal Investigator:** [name], NP

**Co-Principal Investigator:** [name]

the patient's head or face, the patient's eyes will be blacked out.

**5. COMPENSATION FOR INJURIES**

Every effort to avoid side-effects of participating in this research study will be made, but there can be no guarantee that study subjects will not experience some physical damage. As there is no automatic compensation available for physical injury for a research study, study subjects will not be automatically reimbursed for the costs of time lost from work or the costs of extra hospital days, doctor's fees, and medicine.

**6. BENEFITS TO SUBJECT**

No direct benefit can be guaranteed as a result of participation in this research study, however, because UVB Excimer laser is an established therapy for psoriasis, it is anticipated that some participants may see an improvement of their disease. Participation in this study will help aid in the understanding of Excimer lasers and the effects they have on serum inflammatory markers in the body.

**7. COSTS TO THE SUBJECT**

There is no cost to the participant for research-specific procedures. Standard of care procedures will be billed to the subject's insurance.

**8. ALTERNATIVES TO PARTICIPATION**

Alternative treatments available to patients who decide not to participate or who may withdraw early from the study are:

- Topical creams/ointments
- Methotrexate
- Oral retinoids
- Cyclosporine
- Full body narrowband UVB
- Biologics

**9. WITHDRAWAL FROM STUDY PARTICIPATION**

The participants are entitled to withdraw from the study at any time and for whatever reason without this having an effect on their access to the treatment via the investigator.

## **10. PAYMENT TO THE SUBJECTS (REIMBURSEMENT AND INCENTIVES)**

The participant will be compensated for study parking costs (if any); parking validated for study-related visits. Subjects will be compensated \$50 at the screening visit and \$50 at the final visit to cover study-related procedures. All Excimer laser treatment visits will be billable to the patient's insurance company, per standard of care. Participants to choose to participate in the optional sub-study will receive \$20 for each additional blood draw and \$25 for each punch biopsy.

## **11. PLAN FOR OBTAINING INFORMED CONSENT (INFORMED CONSENT PROCESS)**

Potential subjects recruited for study participation will be seen by a member of the study staff in a private exam room for the formal consent process. Each participant will have the study explained in its entirety with special attention to the length of the study, the actual study procedures, financial obligations, risks, benefits and alternatives to participation. Participants will be given ample time to consider study participation and encouraged to discuss with significant others, have any questions answered by the study staff. Only participants willing to undergo all study procedures will be asked to affirm participation by signing the consent form. Only study staff that have been trained on the study and having IRB required Human Subject Protection Training and authorized by the investigator will obtain consent. Subjects will be reminded the importance of adhering to all study requirements and their right to withdrawal at any time without affecting the quality of their individual medical care.

## **12. PROVISIONS FOR SUBJECTS FROM VULNERABLE POPULATIONS**

No special subject populations are targeted for inclusion in this protocol however if subjects from vulnerable populations noted below are eligible, additional procedures will be followed.

In the event that an illiterate person who understands English presents themselves as a potential study participant and they meet all of the inclusion/exclusion criteria, the consent form will be read to that individual in the presence of a witness. The study participant will sign the consent document by "making their mark" in the signature space; the witness must also sign and date the consent form, noting that the informed consent process has taken place.

House staff and students, medical students on a clerkship, and employees of Case Western Reserve University (CWRU) or UHC are not excluded from the study, but their participation will be entirely voluntary. Their scholastic or employment evaluations will be conducted by a rater uninvolved with, and most likely totally unaware of, the study. Members of the study team are not eligible to participate in this study as a subject. Subject participation is kept confidential by the entire study team, and will not be divulged to supervisors, evaluators, or others, unless under the unlikely condition where it becomes medically necessary information, with the subject's consent.

### **13. SUBJECT PRIVACY AND DATA CONFIDENTIALITY**

Study participant information collected in the research process may include; contact information, consent documentation, demographics, social security number (necessary for reimbursement), and personal medical history. All data will be stored on the secure UH or REDCap© server or as paper records stored in a locked cabinet. Data collected in this study will include: Patient records collected electronically and on paper, consent forms, and blood samples. Each class of data will be handled in the following manner:

**13.1 Patient Records and Consent Forms:** Patients enrolled into the study will complete informed consent and provide medical history. All patients upon entering the study will be assigned a unique identifier by REDCap© that will be used throughout the study to de-identify their information. Consent forms and paper records will be filed in study binders, stored in a locked room within the Department of Dermatology. Only authorized research personnel will have access to these records.

Patient records will be created and stored electronically on both the secure and encrypted University Hospitals server and the secure REDCap© server. REDCap serves as the main computerized data management system for this study.

The PI will ensure protocol adherence, proper protocol conduct, data quality, and subject safety and efficacy by conducting regular meetings with the entire study staff. The adverse events submitted by subject phone inquiry or email will be reviewed and adjudicated with all research team members. In addition, any adverse events or deviations to the protocol or other issues will be discussed at the Regulatory Meeting held monthly in the department of Dermatology.

**13.2 Blood Samples:** Study personnel will acquire the specimen from each patient via needlestick, de-identify the specimen using a code specific for this trial before sending it to the lab for processing.

**13.3 Photographs:** All photographs will be de-identified and stored on the secure UH server, only accessible to authorized study personnel. In the event a photograph is taken of the face or any other identifiable feature, the patient's identity may become known.

**13.4 Data Transfer/Transmission:** Research data will be sent to [name], Biostatistical Core, CWRU after finishing the clinical trial; however, all of the data will be stripped of patient identifiers prior to transfer.

In order to comply with federal regulations, records identifying participants in this study may be reviewed authorized representatives of the Institutional Review Board or other federal regulatory officials responsible for oversight of human subject protection. Any data

**University Hospitals Case Medical Center**  
**Department of Dermatology**  
**Protocol**

**Protocol Title:** Effects of UVB Excimer Laser on Serum Inflammatory Markers in Patients with Psoriasis

**Principal Investigator:** [name], NP

**Co-Principal Investigator:** [name]

linking participants to their sample will be de-identified. A code will be used to link participants to identifying information and only the investigators and the research study coordinators will have access to this information, which will be stored on a server at University Hospitals Case Medical Center with a separate encryption code. Upon enrollment, each patient record will be stripped of all identifying information and assigned a unique numerical identifier that has no reference to any identifiable patient information.

## **14. DATA ANALYSIS PLAN**

- 14.1 Clinical Outcome:** Clinical evaluation through PASI scoring and PGA will be performed, supported by photographic documentation. Percent change in PASI and number of treatments to obtain PASI 75 improvement will be calculated for each patient and results summarized as descriptive statistics using means and standard deviations.
- 14.2 Serum inflammatory markers:** Levels of inflammatory markers in the serum e.g. CRP, resistin, MPO and S100. will be quantified pre and post treatment via ELISA kits and correlated with PASI score, total number of treatments received, BMI and nutrition data, using multivariate regression analyses.
- 14.3 Optional flow cytometry analysis:** Populations of monocytes will be characterized in the blood and response to excimer laser expressed in improvement in PASI scores will be correlated with levels of specific pro-inflammatory monocytes using Pearson correlation coefficient. Level of pro-inflammatory monocytes will also be correlated with levels of CRP, resistin, MPO, S100.
- 14.4 Chromameter Assessment:** Hyperpigmentation of treated plaques will be assessed via  $L^*$ .  $L^*$  values of treated plaques will be compared to  $L^*$  values of normal, untreated skin. Erythema of treated plaques will be assessed via  $a^*$ .  $a^*$  values of treated plaques will be compared to  $a^*$  values of normal, untreated skin. These values will also be compared from visit to visit. They will also be correlated with response to treatment.
- 14.5 Patient Satisfaction Questionnaire:** Each item in the survey will be scored from 1-5. Scores will be summarized and descriptive statistics will be used. Satisfaction scores will also be correlated with PASI improvement.

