#### **3.2.2 Excimer Laser Irradiation:** This is a standard clinical procedure approved for the treatment of psoriasis. Initial laser dose will be anywhere from 1-4x the MED,

**University Hospitals Case Medical Center**  
**Department of Dermatology**  
**Protocol**

**Protocol Title:** Effects of UVB Excimer Laser on Serum Inflammatory Markers in Patients with Psoriasis

**Principal Investigator:** [name], NP

**Co-Principal Investigator:** [name]

depending on thickness of the plaque. Escalation will be 25-50% increase in dose per treatment if there is no residual erythema, 25% increase per treatment if there is mild residual erythema, and 0% increase per treatment if there is moderate residual erythema. Investigator also has the option to skip a treatment, if there is above moderate erythema, or significant patient discomfort exists. Patients will receive treatment twice a week until one of the following:

- PASI 75 Improvement
- Patient reaches a maximum of 20 treatments

**3.2.3 Optional Punch Biopsy:** Up to 8mm punch biopsies may be taken at the screening visit and final visit from a psoriasis lesion. The tissue samples will be used for histology and undergo standard H&E staining to evaluate the differences before and after Excimer laser treatment. Patients may still participate in this study if they choose to not donate punch biopsies. This procedure involves the removal of a small circle of skin (pencil eraser-sized) using a cookie cutter-like instrument. Lidocaine is used to numb the area to be removed before obtaining the biopsy and then 1-2 stitches are used per biopsy site to prevent bleeding, speed healing and improve the appearance. This procedure may last up to an hour depending on the number of biopsy sites. The stitches are then removed 7-14 days later.

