**3.2.4 PASI Scoring:** PASI will be determined for all subject at the Screening Visit, Visit 8, Visit 16, at Visit 23 Final/Termination Visit and, if applicable, the 3 month follow-up visit. The PASI is a measure of psoriatic disease severity taking into account qualitative lesion characteristics (erythema, thickness, and scaling) and degree of skin surface area involvement on defined anatomical regions. The PASI is a validated instrument that has become standard in clinical trials for psoriasis. Psoriasis Area Severity Index scores range from 0 to 72, with higher scores reflecting greater disease severity. Erythema, thickness, and scaling are scored on a scale of 0 (none) to 4 (very severe) on 4 anatomic regions of the body: head, trunk, upper limbs, and lower limbs. Degree of involvement on each of the 4 anatomic regions is scored on a scale of 0 (no involvement) to 6 (90% to 100% involvement). The total qualitative score (sum of erythema, thickness, and scaling scores) is multiplied by the degree of involvement for each anatomic region and then multiplied by a constant. These values for each anatomic region are summed to yield the PASI score.

**3.2.5 Physician Global Assessment (PGA):** PGA skin evaluation will be performed at the Screening visit, Visit 8, Visit 16, Visit 23 Final/Early Termination Visit, and, if applicable, the optional 3 month follow-up visit. This assessment is a scale from 0 (clear) to 5 (severe). It is a global assessment of the subject's psoriasis based on the severity of induration, scaling and erythema.

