#### **3.3.3 Treatment Visits (Visits 3-22) (estimated time: up to 1 hour):**

***\*Patients will undergo Treatment twice a week until they reach a PASI 75 improvement, or until they reach the maximum of 20 total treatments\****

- Study staff will review concomitant medications, any AEs since the previous visit, and procedures with each subject.
- Subjects will have their psoriasis clinically evaluated through PASI scoring and PGA every four weeks during Visit 8 and Visit 16.
- During Visit 8 and Visit 16, treated plaques will be evaluated using a chromameter to measure hyperpigmentation and erythema that may be caused by the laser.
- Subjects will have plaque/body photographs throughout this study.
- Subjects will undergo standard clinical treatment with an Excimer Laser.

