**University Hospitals Case Medical Center**  
**Department of Dermatology**  
**Protocol**

**Protocol Title:** Effects of UVB Excimer Laser on Serum Inflammatory Markers in Patients with Psoriasis

**Principal Investigator:** [name], NP

**Co-Principal Investigator:** [name]

**3.3.4 Visit 23: Final Visit/Early Termination Visit [2 days-2 weeks after last treatment]  
(estimated time: up to 1 hour )**

- Subjects will have their psoriasis clinically evaluated through PASI scoring and PGA.
- Treated plaques will be evaluated using a chromameter to measure hyperpigmentation and erythema that may be caused by the laser.
- Subjects may have plaque/body photographs taken.
- Subjects will undergo a post-treatment blood draw.
- Optional, post-treatment punch biopsies may be taken from a psoriasis lesion.
- Subjects will fill out the Patient Satisfaction Survey.

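### Section 14.1 takes a mean and SD of treatments to PASI 75 over all patients, but patients who never reach PASI 75 have no such number

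*Combined protocol and SAP*

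**What the plan says.** Section 14.1 (Clinical Outcome) names two quantities, percent change in PASI and a treatment count. For the second, the "number of treatments to obtain PASI 75 improvement will be calculated for each patient", with "results summarized as descriptive statistics using means and standard deviations".

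Section 3.3.3 gives treatment twice a week "until they reach a PASI 75 improvement, or until they reach the maximum of 20 total treatments". Section 3.2.2 lists the same two ways to stop, the second being "Patient reaches a maximum of 20 treatments". Section 9 adds that "The participants are entitled to withdraw from the study at any time and for whatever reason".

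On when response can be seen, section 3.2.4 states that "PASI will be determined for all subject at the Screening Visit, Visit 8, Visit 16" and at the Visit 23 final or termination visit, with an optional 3-month follow-up. Section 3.3.4 places Visit 23 "2 days-2 weeks after last treatment". The schedule of events in section 3.4 shows no PASI at the other treatment visits. Section 3.2.2 also says that the "Investigator also has the option to skip a treatment" in the event of marked erythema or discomfort.

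No section gives a value to patients who do not reach PASI 75, restricts the summary to responders, or plans a censored analysis.

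**The concern.** The stopping rule provides for patients who finish without PASI 75. For someone who has had 20 treatments without response, all that is known is that the number needed is more than 20, or that no number would suffice. For someone who withdraws earlier without response, only a lower bound is known. A mean over every patient cannot be computed from such data without a rule, and the plan gives none. The analyst would have to choose one after the data are in.

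Both obvious choices mislead if reported simply as the mean number of treatments to PASI 75. A responders-only mean does not depend on how many responded: 6 of 24 patients responding after an average of 10 treatments gives the same figure as 24 of 24 doing so. Entering 20 for the rest treats a lower bound as an observed value. Section 14.1 does not ask for the proportion reaching PASI 75, which would tell these situations apart.

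**Working it through.** **1. The plan's own figure.** Visits 3 to 22 are treatment visits: 22 − 3 + 1 = 20, which matches the stated maximum. No stated number is wrong; the gap is in the analysis rule.

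**2. Who has a value.**
- Stopped for PASI 75: yes.
- Stopped at 20 treatments without PASI 75 (sections 3.2.2 and 3.3.3): no, only a lower bound.
- Withdrew without PASI 75 (section 9): no, only a lower bound.

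**3. How far the choice of rule moves the mean.** Let m be the mean count among responders and p the fraction of patients without PASI 75. The documents give neither, so the values below are assumptions.
- Non-responders left out: mean = m, whatever p is.
- Non-responders counted as 20: mean = (1 − p)m + 20p, so the shift is p × (20 − m).

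| Assumed m | Assumed p | Left out | Counted as 20 | Shift |
|---|---|---|---|---|
| 14 | 10% | 14.0 | 14.6 | +0.6 |
| 10 | 25% | 10.0 | 12.5 | +2.5 |
| 10 | 50% | 10.0 | 15.0 | +5.0 |
| 6 | 50% | 6.0 | 13.0 | +7.0 |

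In patients, the second row with N = 24 is 18 responders and 6 non-responders: (18 × 10 + 6 × 20)/24 = 300/24 = 12.5.

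**4. What a proportion would look like at the planned size** (24 to 27 patients, section 3). Exact (Clopper-Pearson) 95% CIs:
- 6/24: 9.8% to 46.7%
- 12/24: 29.1% to 70.9%
- 18/24: 53.3% to 90.2%
- 20/27: 53.7% to 88.9%

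**5. Caveat on the responders' own counts.** With no skipped sessions, treatment number = visit number − 2, so Visit 8 is treatment 6, Visit 16 is treatment 14 and Visit 22 is treatment 20. If PASI 75 is judged only at scheduled scorings, a responder's count is known only to lie within 1–6, 7–14 or 15–20. If PASI is scored before that day's laser session, the bands are 1–5, 6–13 and 14–20. The widest band holds 8 treatments either way, so a recorded count could be at most 7 later than the true one. If response is judged at every session, this lateness is about zero.

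**The case against.** The best defence is that the phrase naturally means the patients who obtained PASI 75, and that a descriptive table would normally show its n. Section 14.1 also summarises percent change in PASI, which would usually differ between a cohort with few responders and one with many. Both points reduce the harm. They do not remove it: the plan says each patient, does not ask for n, and percent change does not give the proportion at PASI 75.

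An average capped at 20 can be defended as a restricted mean if it is labelled so. The plan does not label it, and patients who withdraw before 20 would still need a further assumption.

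It is also fair that treatments received when PASI 75 is first recorded is a legitimate operational count, and that an interval-censored model is more than 24 to 27 patients need. Both points stand, and the fix follows them.

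A reader might infer more than the documents support in two ways:
- **That the recorded counts are necessarily several treatments late.** This needs response to be judged only at scheduled scorings, which the plan does not say. Treatment runs until PASI 75 is reached, and the early-termination visit includes PASI, so judgement between scheduled scorings is possible. Skipped sessions and the order of scoring and laser would also move the bands.
- **That the trial's aims are compromised.** The aims in section 2 concern serum markers, erythema and hyperpigmentation. The total number of treatments received, used in section 14.2, is counted directly and exists for every patient.

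**Conclusion.** The concern holds for one descriptive outcome. Under any reading of the visit schedule, the number of treatments to PASI 75 is right-censored for patients who reach 20 treatments or withdraw without response, and the plan's mean and SD have no rule for them. The size cannot be fixed from the documents: the two obvious rules differ by p × (20 − m), which is 0.6 to 7.0 treatments over the assumed ranges m = 6 to 14 and p = 10% to 50%, and zero if every patient responds. The band argument is a caveat that depends on how response is judged. No sample size, test, safety rule or stated hypothesis rests on this mean, so this is a minor improvement that is worth making because it costs little.

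**What to change.** In section 14.1:
- Report n/N and the proportion of all treated patients reaching PASI 75 by the final visit, and cumulatively by Visits 8 and 16, with exact 95% CIs. Patients stopped early for PASI 75 stay counted as responders. Withdrawals without PASI 75 count as not reached. Make this the leading summary.
- Replace the mean and SD of the count with a Kaplan-Meier summary of treatments received when PASI 75 was first recorded. Censor patients without PASI 75 at the treatments received by their last PASI. If the curve does not reach one half, report the median as not reached. State that this treats withdrawal as unrelated to response, an assumption that the proportion above does not make.
- At minimum, if the Kaplan-Meier summary is not wanted, give the count among responders only, labelled as such and shown beside n/N.

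In sections 3.2.2 and 3.3.3, add one sentence: stopping for PASI 75 requires a recorded PASI score, entered with the number of treatments received. State whether this may happen between the scheduled scorings; that settles the band caveat.

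The cost is wording and a little analysis time. The PASI scores in section 14.1 are already planned, and no visit is added. The downside is a summary that looks less precise: with 24 patients, 12 responders give an interval of about 29% to 71%.

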## **2. STUDY OBJECTIVES/HYPOTHESIS**

The overall aims for this study are to determine whether UVB excimer laser treatment of psoriasis affects serum inflammatory markers, and to assess hyperpigmentation and erythema with excimer laser treatment.

We hypothesize that treatment of psoriasis with UVB delivered via 308 nm excimer laser will decrease the levels of serum inflammatory markers. We hypothesize that treatment will decrease plaque erythema and will result in minimal hyperpigmentation

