**University Hospitals Case Medical Center**  
**Department of Dermatology**  
**Protocol**

**Protocol Title:** Effects of UVB Excimer Laser on Serum Inflammatory Markers in Patients with Psoriasis

**Principal Investigator:** [name], NP

**Co-Principal Investigator:** [name]

**3.2.6 Chromameter Assessment:** Treated plaques will be evaluated using a chromameter as an objective measure of hyperpigmentation and erythema at Screening Visit, Visit 8, Visit 16, Visit 23 Final/Early Termination Visit, and, if applicable, the 3 month follow-up visit. The chromameter uses the L\*a\*b\* color system. L\* measures skin reflectance or lightness, a\* measures red to green color saturation, b\* measures yellow to blue color saturation. Hyperpigmentation of treated plaques will be assessed via L\*. L\* values of treated plaques will be compared to L\* values of normal, untreated skin. Erythema of treated plaques will be assessed via a\*. a\* values of treated plaques will be compared to a\* values of normal, untreated skin. These values will also be compared from visit to visit.

**3.2.7 Limited Medical Exam:** Medical and Dermatological history, demographic information, concomitant medications, vital signs, height, weight, and BMI will be collected during Visit 1/Screening Visit.

**3.2.8 Blood Draw:** Blood will be drawn at Visit 1/Screening Visit and at Visit 23 Final/Early Termination Visit by venipuncture and will be evaluated for:

- Serum Inflammatory Markers: (e.g. Levels of CRP, resistin, MPO and S100, etc) as quantified via ELISA kits [ $\sim$ 10mL blood].
- Pro-Inflammatory Monocytes (optional): Populations of monocytes will be characterized in the blood and via flow cytometry analysis [ $\sim$ 60mL blood].

**3.2.9 Questionnaires:** Subjects will be asked to complete two questionnaires.

**3.2.5.1 Patient Satisfaction Survey:** Patients will be asked to complete a survey, scoring their satisfaction with the treatment at Visit 23 Final/Early Termination Visit.

**3.2.5.2 Nutrition Questionnaire:** Patients will be asked to complete a survey about their nutritional habits at Visit 1/Screening Visit.

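### The first hypothesis is that serum markers fall, but the planned marker analysis (14.2) is correlation and regression only and need not estimate the change

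*Combined protocol and SAP*

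**What the plan says.** Section 2 puts the markers first: "The overall aims for this study are to determine whether UVB excimer laser treatment of psoriasis affects serum inflammatory markers". The hypothesis has a direction, namely that treatment "will decrease the levels of serum inflammatory markers".

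Section 3.2.8 provides the data for a before-and-after comparison: "Blood will be drawn at Visit 1/Screening Visit and at Visit 23 Final/Early Termination Visit by venipuncture".

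The available text analyses the markers in two places. Section 14.2 says the levels "will be quantified pre and post treatment via ELISA kits and correlated with PASI score, total number of treatments received, BMI and nutrition data". The only method it names for doing this is given as "using multivariate regression analyses". Section 14.3, for the optional sub-study, adds: "Level of pro-inflammatory monocytes will also be correlated with levels of CRP, resistin, MPO, S100".

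Other outcomes in section 14 do get a comparison over time. For PASI, 14.1 says: "Percent change in PASI and number of treatments to obtain PASI 75 improvement will be calculated for each patient". For the chromameter values, 14.4 says: "These values will also be compared from visit to visit".

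**The concern.** The question in section 2 is whether markers fall on average. The question in 14.2 is which patient characteristics go with marker values. That second question is legitimate and fits the mechanism in section 1, where less skin inflammation leads to less systemic inflammation. It does not replace the first.

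The two can come apart in either direction. If every patient's marker fell by the same amount, the change would correlate with nothing. If markers did not fall on average but patients with more PASI improvement fell and the rest rose, the correlation could be strong.

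Because 14.2 leaves the response and the model form open, they could also be chosen after the data are seen, for at least four markers.

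**Working it through.** The plan gives no power, alpha, effect size or SD for the markers, so there is no stated figure to reproduce.

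**Inputs from the documents**
- 24 to 27 patients in one group (section 3).
- Two marker measurements per patient, at Visit 1 and Visit 23 (3.2.8).
- Four named covariate types: PASI, number of treatments, BMI and nutrition (14.2).

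**Assumptions**
- Two-sided alpha of 5%, 80% power and complete pairs.
- Mean change expressed in SDs of the within-patient change.

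**Step 1: algebra.** Let D = post − pre for each patient and x be a covariate. The slope is Σ(x − x̄)(D − D̄) / Σ(x − x̄)². Adding a constant c to every D moves D̄ by c and leaves every (D − D̄) as it was. The slope, its p-value and the correlation therefore do not move. The same holds if the response is the post level.

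**Step 2: numerical check of step 1.** One simulated data set of 24 patients and four covariates was refitted with a common shift added to the post values.

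| Shift | Mean change | Paired p | Joint p for slopes, response = change | Joint p for slopes, response = post level |
|---|---|---|---|---|
| 0 | −0.45 | 0.21 | 0.002 | 0.067 |
| −3 | −3.45 | 1×10⁻⁹ | 0.002 | 0.067 |
| +3 | +2.55 | 2×10⁻⁷ | 0.002 | 0.067 |

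Only the intercept responded. It equals the mean change only if the response is the change and the covariates are centred. In a further fit with two covariates and a sample mean change of −3.45, the centred intercept was −3.45 (SE 0.36). The uncentred intercept was −4.99 (SE 2.68).

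**Step 3: how often each analysis gives p<0.05 (n = 24).** The table uses 20,000 runs, or 8,000 for the four-covariate rows.

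| Analysis | Mean change 0 | −0.6 SD | −1.2 SD |
|---|---|---|---|
| Paired test | 5% | 80% | 100% |
| Correlation of change with one covariate, true correlation 0 | 5% | 5% | 5% |
| Same, true correlation 0.3 | 30% | 31% | 30% |
| Same, true correlation 0.5 | 73% | 73% | 73% |
| Joint test of four slopes, covariates unrelated to change | 5% | 6% | 5% |
| Intercept, change as response, four centred covariates | 5% | 80% | 100% |

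The four covariates were given assumed distributions: PASI 10 (SD 3), 8 to 20 treatments, BMI 30 (SD 6) and one nutrition score.

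**Step 4: levels regressed on PASI.** PASI is scored at both blood-draw visits and should itself fall, so this form needs separate treatment. Assume baseline PASI 8 (SD 2), falling to 20–50% of baseline.
- *Pre and post values pooled, pairing ignored.* At −0.6 SD, p<0.05 occurs in 52%, 26% or 5% of runs when the between-patient SD is 0.5, 1 or 2 times the change SD. With no fall, the rejection rate is below the nominal 5%.
- *Pairing respected (within-patient regression on PASI).* p<0.05 occurs in 5%, 77% and 100% of runs at 0, −0.6 and −1.2 SD.

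**Step 5: what a stated paired analysis would deliver.**
- The change detectable with 80% power (noncentral t) is 0.597 SD at n = 24 and 0.560 SD at n = 27.
- The 95% CI half-width is t(0.975, n−1)/√n, in SDs of the change: 2.069/√24 = 0.422 and 2.056/√27 = 0.396.

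**The case against.** The best defence is that a pre/post comparison is implied. Section 2 hypothesises a decrease, exactly two draws are scheduled, 14.2 mentions both time points, and nothing prevents the change from being reported. On this view the plan is under-specified and does not contradict its aim. It is true that the data will exist. But in 14.2 the time points describe when levels are measured, while the analysis named is correlation by regression. Sections 14.1 and 14.4 show that the authors write a comparison over time where they intend one.

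The second argument is stronger: the insensitivity in step 1 does not extend to every regression that 14.2 could mean. A within-patient regression of levels on PASI does respond to a fall, with nearly the power of the paired test (77% against 80% at −0.6 SD). Change regressed on centred covariates, or pre and post as joint responses with a within-patient contrast, recovers the mean change exactly. This stands, and it is why the point is that the plan *need not* estimate the change, not that it cannot. But 14.2 commits to none of these forms, and the PASI slope assumes the marker tracks PASI and is not an estimate of mean change.

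Third, the 73% is not an error rate. It is the power to detect a true correlation of 0.5, which is a correct answer to a different question. It misleads only if such a result is read as evidence that markers fell. That is accepted.

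Finally, in a small uncontrolled study with no named primary endpoint, one may ask how much this matters. It concerns the first aim, and the repair is very cheap.

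**Conclusion.** The concern holds. No available section states a mean or percent change, a confidence interval, a paired test, a time term or a response variable for the markers. The stated method can therefore be completed without answering the first hypothesis.

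The size depends on which model is eventually fitted. At a true fall of 0.6 SD with 24 patients, the chance of a result with p<0.05 that reflects the fall ranges from none (any slope or correlation on the change) to 80% (paired test or an equivalent contrast). Regressions of level on PASI lie between these, at 5% to 77% under the PASI and variance assumptions above.

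The insensitivity of change-on-covariate slopes is algebraic and needs no assumption. The percentages rest on the assumed alpha, effect sizes, correlations and variances, because the documents give none. This should be corrected before the markers are analysed.

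**What to change.** In 14.2, state that the main analysis for each marker is the within-patient change from Visit 1 to Visit 23, reported with a 95% CI and a paired test, on the log scale if the data are skewed. Keep the regressions and correlations in 14.2 and 14.3 as exploratory, and state for each whether the outcome is the change or a level.

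With no control group, describe any fall as a change over time and not as an effect shown to be due to the laser.

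Three separate, optional additions would help: name a lead marker, adjust the others for multiplicity, and say which S100 protein is measured. Four independent tests at 5% carry a familywise error of 1 − 0.95⁴ = 18.5%. At 0.05/4 = 0.0125 per marker, the change detectable with 80% power becomes 0.73 to 0.68 SD for 24 to 27 patients.

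The cost is a sentence or two of wording and minor extra analysis. Both draws are already scheduled, so no patients, visits or samples are added.
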